This prospective, blinded, randomized, placebo-controlled pilot study will evaluate the effect of astaxanthin in reducing inflammation, controlling pain, and improving physical function in patients with advanced knee osteoarthritis awaiting total joint replacement surgery. Levels of pro- and anti-inflammatory cytokines and chemokines will be measured following the completion of a daily oral regimen of astaxanthin vs. placebo. Additionally, patient-reported outcome measurements assessing physical function and pain interference will be obtained prior to and following completion of treatment allowing for a comparison between treatment groups. Study outcomes will provide evidence to support astaxanthin supplementation as a cost-effective, added strategy for symptom management in patients with advanced osteoarthritis and will lay the foundation to seek additional federal funding to conduct a large-scale clinical trial to further establish the efficacy of this treatment strategy.

2. Objectives / Research Aims

The goals of this study are to:

- a. Determine the effect of astaxanthin on pain control and physical function in patients with osteoarthritis who are scheduled to undergo a total knee replacement surgery.
- b. Determine the effect of astaxanthin on inflammatory synovial markers in patients with osteoarthritis who are scheduled to undergo a total knee replacement surgery.

3. Setting

This study will take place at Prisma Health Orthopedics clinic facilities and Prisma Health Baptist Hospital.

4. Resources Available

Documentation will be comprised of a thorough history and physical, clinical progress notes, operative reports, anesthesia reports, and post-operative progress notes available on the EPIC EMR as well as patient reported outcome measurements collected via PROMIS surveys and stored on the Prisma Health REDCap server, a secure data collection platform.

Two fellowship trained orthopaedic surgeons will lead the research team.

The research team will be comprised of practicing orthopaedic surgeons, the Chair of the Department of Pathology, Microbiology, and Immunology, resident orthopaedic surgeons in training, medical students, clinical nursing staff, and research assistants.

5. Study Design

This will be a prospective, double-blinded, randomized, placebo-controlled pilot study.

a. Recruitment Methods

Adult patients with advanced osteoarthritis who are scheduled to undergo total knee replacement surgery, meeting all inclusion/exclusion criteria, will be approached by a study team member. The team member will review the study with the patient and, if appropriate, obtain their consent to participate in the study.

b. Inclusion and Exclusion Criteria

Inclusion:

- ≥ 18 years of age
- Radiographic evidence of advanced knee osteoarthritis
- Knee pain
- Scheduled to undergo a total knee replacement

Exclusion:

- < 18 years of age
- Unable to provide written consent
- Known allergy to fish or astaxanthin
- Pregnant and/or breastfeeding
- Received a corticosteroid injection within 3 months of initiating treatment with astaxanthin or placebo
- Currently taking immunosuppressant drugs or drugs which act as a 5-alpha reductase inhibitor

- History of any autoimmune condition
- Known autoimmune etiology for arthritis (e.g. Rheumatoid or Psoriatic arthritis)

c. Number of Subjects

160 total patients included in this study, 80 per treatment arm.

d. Study Procedures

Once patients have been enrolled in the study, they will complete a Patient Reported Outcome Measurement Information System (PROMIS) Physical Function and Pain Interference assessment. This assessment will be administered on an iPad by clinic or research staff and data will be recorded in REDCap.

Participants will be randomized to receive a daily oral regimen of either astaxanthin (12mg) or placebo over a 6-week period prior to surgery. Patients will record compliance with taking the supplement via a log provided to them at the time of consent.

Research staff will call participants biweekly over the 6-week period to assess pain score, supplement compliance and record any side effects from the astaxanthin or placebo.

On the day of surgery, participants will again complete the PROMIS Physical Function and Pain Interference assessment when they arrive at the hospital. This assessment will be administered on an iPad by clinic or research staff and data will be recorded in REDCap.

At the time of surgery, following sedation, an aliquot of synovial fluid will be collected from the affected knee by the orthopedic surgeon performing the surgery. Obtained samples will be analyzed to measure levels of pro- and anti-inflammatory cytokines and chemokines.

e. Study Timelines

Following IRB approval, we will begin prospectively enrolling eligible patients in this study. Currently, [name] treats approximately 50 patients in clinic per week, with nearly 50% suffering from knee osteoarthritis. Overall, he performs 2-6 knee replacements for advanced osteoarthritis per week. Given the high volume of patients treated by [name] with advanced osteoarthritis who will ultimately undergo total knee replacement surgery, we expect to achieve complete enrollment of 160 participants in a 10-12-month period. Additional orthopedic surgeons may be included to increase enrollment, if necessary.

Following the completion of participant enrollment and data collection, the

obtained results will be reviewed and statistically analyzed over a 2-month period.

f. Study Endpoints

Pain interference and physical function between the astaxanthin and placebo control group as measured by PROMIS Physical Function and Pain Interference assessments prior to beginning astaxanthin or placebo treatment regimen and just prior to surgery.

Inflammatory profiles of post-treatment synovial fluid from the astaxanthin and placebo control group as measured by levels of pro- and anti-inflammatory chemokines and cytokines.

g. Medication Treatment protocol

Pre-Operatively:

12mg Astaxanthin or placebo once daily for 6 weeks prior to surgery

h. Data Collection/Banking

All data will be stored on a password-protected, encrypted spreadsheet. Only members of the study team will have access to this information.

Participants will be given a unique study ID and a separate password-protected document will be created linking patients to their study ID.

Data recorded via PROMIS and phone surveys will be stored on the Prisma Health REDCap sever, a secure web application for managing research databases.

Synovial fluid samples will be stored in a -80C freezer in a locked laboratory and will only be accessible to members of the study team. Samples will be labeled with study IDs given to participants.

i. Statistical Analysis

PROMIS assessments will be completed at two time points: prior to beginning the astaxanthin or placebo treatment regimen and just prior to surgery, at the time of completing the treatment regimen. A paired t-test will be performed to detect differences in the before and after measurements per group. These differences will then be compared for patients in the astaxanthin arm vs. placebo arm to determine if participants receiving astaxanthin report a significant difference in pain and physical function ability following completion of the treatment regimen.

Synovial fluid will be collected in heparinized tubes at the time of surgery. A quantitative analysis of immune cell infiltration will be performed from the synovial fluid collected, using a hematology analyzer. This will provide total and

differential WBC counts. Further studies will be done to estimate the cytokine and chemokine levels in synovial fluid. Statistical analysis will be performed and a p value < 0.05 between groups will be considered statistically significant.

j. Data Management

Data will be maintained on a secure password protected server. Only IRB authorized research study members can access this information. The researchers involved in this study commit to handle all information with care and to protect research subjects' identity. The data collected will be kept for at least three years after publication and then destroyed in accordance with the hospital and federal guideline. Participants will be given a unique study ID and a separate password-protected document will be created linking patients to their study ID. No PHI will be disclosed during statistical analysis or subsequent presentations or publications.

k. Confidentiality

All study related data activities will take place on password-protected network supported by the home hospital institution. Study team has been educated and agrees to uphold the hospital and federal confidentiality laws.

l. Provisions to Monitor the Data to Ensure the Safety of Subjects

Data will be maintained on a secure server with password protection. Study data and signed consent documents will be stored in a locked office in Prisma Health Orthopedics. Only authorized research members of this study can access this information. The researchers involved in this study commit to handle all information with care and to protect research subjects' identities.

6. Risks to Subjects

Possible side effects associated with Astaxanthin supplementation are increased bowel movements, red stool color, and stomach pain.

Astaxanthin has been shown to hinder the 5-alpha reductase enzyme in laboratory studies. This may prevent testosterone from changing into the dihydrotestosterone (DHT) hormone. While it is unclear the exact effect that astaxanthin may have due to this interaction, similar medications that affect the 5-alpha reductase enzyme may cause side effects such as lower libido, male breast growth, and erectile dysfunction. Patients who are currently taking medication which acts as a 5-alpha reductase inhibitor will be excluded from this trial.

Astaxanthin has the potential to increase the function of your immune system. Patients who are currently taking immunosuppressant drugs and/or have an autoimmune condition will be excluded from this trial.

As this is a prospective study, there is a slight risk of loss of confidentiality of protected health information (PHI). Members of the study team commit to handle all information with care and protect the identify of research subjects.

7. Potential Benefits to Subject

Patients may potentially benefit by receiving a new regimen of medical care that reduces the inflammation associated with advanced osteoarthritis, subsequently reducing pain improving physical function.

Indirectly, patients may benefit by providing information for medical professionals to better treat patients in the future.

8. Consent Process

During the pre-operative phase, in clinic, eligible patients will be identified. A member of the study team will explain the purpose of the research and what the patient's role will be. The person obtaining consent will adequately review all potential risks and benefits and will not coerce patients to consent. This is outlined on our informed consent document. Written informed consent will be obtained on our informed consent document. These documents will be stored in a locked office Prisma Health Orthopedics Research Department as well as the subject's electronic medical record. Participants will also be provided a signed copy of the informed consent document to keep.

9. Bibliographic References

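### Current users of non-study astaxanthin are not excluded and the described procedures do not ask about such use, so any dilution of the contrast would go unrecorded

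*Combined protocol and SAP*

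**What the plan says.** All references are to the combined protocol and SAP.

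- **Eligibility (section 5.b).** Astaxanthin appears once as a reason for exclusion: "Known allergy to fish or astaxanthin". The criterion on concurrent products is "Currently taking immunosuppressant drugs or drugs which act as a 5-alpha reductase inhibitor". The only look-back period is for steroid injections: "Received a corticosteroid injection within 3 months of initiating treatment with astaxanthin or placebo".
- **Treatment (section 5.d).** "Participants will be randomized to receive a daily oral regimen of either astaxanthin (12mg) or placebo over a 6-week period prior to surgery".
- **Monitoring (section 5.d).** "Patients will record compliance with taking the supplement via a log provided to them at the time of consent". Staff telephone every two weeks "to assess pain score, supplement compliance and record any side effects from the astaxanthin or placebo".
- **Risks (section 6).** "Astaxanthin has been shown to hinder the 5-alpha reductase enzyme in laboratory studies", followed by "Patients who are currently taking medication which acts as a 5-alpha reductase inhibitor will be excluded from this trial".
- **Outcomes (sections 5.d, 5.f and 5.i).** PROMIS is measured before treatment and on the day of surgery, and the before-after differences are compared between arms. Synovial fluid is taken once, at surgery.

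**The concern.** The opening summary presents the product as a supplement, so a candidate could already be taking it or could start it during the trial. As section 5.b is written, such a candidate is eligible. The procedures in section 5.d record whether the assigned product was taken, but not whether astaxanthin came from another source.

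Both aims in section 2 are to determine the effect of astaxanthin, so both depend on the arms differing in exposure to it. Randomisation balances the expected number of users between arms and so guards against confounding. It does not restore the contrast among those users. If use were more than trivial, the estimated effect would tend to be too small, and without a record of use no count or sensitivity analysis could be produced afterwards. The summary says the pilot is to lay the ground for a larger trial, so an effect that is too small could carry over into that planning.

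**Working it through.** **1. Does any provision already cover non-study use?**

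- The allergy criterion does not concern use.
- The 5-alpha reductase criterion is the nearest candidate, because section 6 says astaxanthin affects that enzyme in the laboratory. But section 5.b speaks of drugs and section 6 of medication, and neither extends the criterion to astaxanthin itself.
- Section 4 lists a history and physical among the records available. No section directs staff to extract supplement use from it.
- The log and calls concern compliance with the assigned supplement, pain score and side effects.

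Nothing in the text reliably excludes users or records use.

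**2. By which route would each outcome be diluted?**

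| Outcome | Type of user | Route |
|---|---|---|
| Synovial markers (one post-treatment sample) | Established or new | Placebo users are exposed to the product; there is no baseline sample to adjust with |
| PROMIS change | Starts during the 6 weeks | Placebo users may gain some of the effect between the two assessments |
| PROMIS change | Established, continuing | Any benefit is already in the baseline score, so users in the astaxanthin arm may change less |

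In the last row the placebo user is not the source of dilution. Any benefit is in both the before and the after score and cancels in the difference.

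**3. How large could it be?**

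Inputs from the documents: 80 per arm (section 5.c) and a 0.05 threshold (section 5.i). There is no power calculation to reproduce, because no effect size, SD or power is given.

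Assumptions: a two-sided test, 80% power with no non-study use, and a share c of patients in each arm who are users and contribute no contrast.

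Standardised effect detectable with 80% power, normal approximation:

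d = (1.960 + 0.842) × √(2/80) = 2.802 × 0.158 = 0.443.

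With the noncentral t distribution (158 degrees of freedom), d = 0.446. The diluted effect is d × (1 − c), and the sample size needed to restore the power is multiplied by 1/(1 − c)².

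| c | Expected users among 80 on placebo | Diluted effect | Power | Multiplier | n per arm to restore 80% |
|---|---|---|---|---|---|
| 0% | 0 | 0.446 | 80% | 1.00 | 80 |
| 1% | 0.8 | 0.442 | 79% | 1.02 | 82 |
| 2% | 1.6 | 0.437 | 78% | 1.04 | 84 |
| 5% | 4 | 0.424 | 76% | 1.11 | 89 |
| 10% (hypothetical) | 8 | 0.401 | 71% | 1.23 | 99 |
| 20% (hypothetical) | 16 | 0.357 | 61% | 1.56 | 125 |

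**4. Does the assumed starting power matter?**

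With a true effect of 0.5 SD, power goes from 88.5% with no use to 87.3% at 2% and 85.2% at 5%. With 0.3 SD, it goes from 47.5% to 46.0% and 43.7%. The loss at 5% use is 3 to 4 points in each case.

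**The case against.** The strongest case on the other side is that the size is entirely assumed. The documents give no share of users, effect size or planned power, and nothing in them supports 10% or 20% use. At 1 to 2%, about one or two of the 80 placebo patients, the loss is under 2 points of power. Treating any use, at any dose or regularity, as removing all contrast is also the severe end of the range. This stands, and it is why the figures are illustrations only.

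A reader might infer that any current user given placebo dilutes the PROMIS result by receiving the test product as a control. The analysis does not support that. Section 5.i compares before-after change, and an established user who continues on placebo changes like any other placebo patient. If established users in the astaxanthin arm gained the full effect from the study product, PROMIS would not be diluted by established use at all.

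A reader might also infer that dilution is actually present, or that use is certain to go undetected. Neither is shown. No use is documented, the consent form, call script and log form were not available for this review, and the medical record may hold supplement use. What can be said is that the procedures as described do not ask.

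A strict screener might turn users away under the 5-alpha reductase criterion, but its wording leaves that to chance. Finally, in a blinded randomised pilot this kind of use pulls towards no difference and would not by itself create a false positive. That limits the consequence but does not remove the gap.

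**Conclusion.** The gap holds on the text: current users of non-study astaxanthin are eligible, and the described procedures neither discourage nor record such use. Dilution is conditional on use occurring, and its route differs by outcome. Under the stated assumptions it costs about 1 to 2 points of power at 1 to 2% use and about 4 points at 5%. The 10 to 20% rows (71% to 61% power) are a hypothetical upper range. This is a worthwhile, inexpensive improvement to the design, not a threat to the trial's validity, and confidence that it has a material effect is low.

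**What to change.** - **Section 5.b:** add an exclusion for anyone currently taking a supplement that contains astaxanthin. Whether to add a look-back period for recent use, and how long, is for the investigators to set.
- **Section 5.d:** at consent, ask participants not to take non-study astaxanthin during the 6 weeks. Ask about its use at consent, on each planned call and on the day of surgery.
- **Section 5.i:** report the number of users by arm, and keep all randomised patients in the main comparison.

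The cost is one eligibility line, one request at consent and one question at contacts that already take place. The downside is losing the few candidates who already take the product. If use proves negligible, the recorded count lets the sponsor show it.

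### Does the pain score taken by telephone during treatment need a baseline value, a defined scale and a planned analysis?

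*Combined protocol and SAP*

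**What the plan says.** Objective (a) in section 2 is to "Determine the effect of astaxanthin on pain control and physical function in patients with osteoarthritis" awaiting knee replacement. Section 5.d sets out the assessments in order:

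- At enrolment, "they will complete a Patient Reported Outcome Measurement Information System (PROMIS) Physical Function and Pain Interference assessment".
- During the regimen, "Research staff will call participants biweekly over the 6-week period to assess pain score"; the same sentence adds compliance and side effects.
- At the end, "On the day of surgery, participants will again complete the PROMIS Physical Function and Pain Interference assessment when they arrive at the hospital".

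The clinical endpoint in section 5.f is "Pain interference and physical function between the astaxanthin and placebo control group as measured by PROMIS Physical Function and Pain Interference assessments", taken before treatment starts and just before surgery. The other endpoint is the synovial cytokine and chemokine profile.

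Section 5.i analyses the two PROMIS time points: a paired t-test within each group, then a comparison of the differences between arms, to see whether astaxanthin participants "report a significant difference in pain and physical function ability following completion of the treatment regimen". The synovial data follow. The only other mention of the calls is in section 5.h: "Data recorded via PROMIS and phone surveys will be stored on the Prisma Health REDCap sever".

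**The concern.** The telephone score is the only item the protocol calls a pain score, and the only pain measurement made while participants are on treatment. It is collected and stored, yet it has no endpoint and no analysis. The scale is not named. *Biweekly* can mean every two weeks or twice a week. Enrolment lists PROMIS alone, so there is no value of the same score before the first dose.

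Three things would be at stake if the score were meant as an outcome:

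- A baseline on the same scale cannot be collected later.
- With no scale, call or contrast fixed in advance, a later report could pick whichever gave the better result.
- Pain interference describes the effect of pain on the person, which need not match a pain score, so the calls might be thought to hold information on objective (a) that the plan leaves unused.

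**Working it through.** **Is objective (a) left without a pain analysis?** No. Set side by side, sections 5.d, 5.f and 5.i agree. PROMIS Pain Interference is measured at enrolment, measured again on the day of surgery, listed as an endpoint and compared between arms. In 5.i, the phrase about pain after completing the regimen closes the description of the PROMIS differences, so PROMIS answers that question. Nothing in this chain uses the calls.

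**How many calls?** Every two weeks over 6 weeks gives 6/2 = 3 calls per participant, or 3 × 160 = 480 in all. Twice a week gives 6 × 2 = 12 per participant, or 12 × 160 = 1,920. The wording allows both, but no planned analysis changes with the answer.

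**What would a same-score baseline buy if the score were analysed?** The plan gives no figure to reproduce here.

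Inputs:
- 80 per arm (section 5.c).
- SD set to 1.
- ρ = correlation of the telephone score with its own baseline (assumed).
- r = correlation of the telephone score with baseline PROMIS Pain Interference (assumed).

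The contrast is the between-arm difference at the last call, with variance factor v. The 95% CI half-width is 1.96 × √(2v/80).

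| Covariate | v | Half-width (SD) |
|---|---|---|
| None | 1 | 0.310 |
| Same score, ρ = 0.3 | 1 − 0.09 = 0.91 | 0.296 |
| Same score, ρ = 0.5 | 1 − 0.25 = 0.75 | 0.268 |
| Same score, ρ = 0.6 | 1 − 0.36 = 0.64 | 0.248 |
| Same score, ρ = 0.7 | 1 − 0.49 = 0.51 | 0.221 |
| PROMIS, r = 0.3 | 0.91 | 0.296 |
| PROMIS, r = 0.5 | 0.75 | 0.268 |

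Against no covariate, the equivalent size is 80/(1 − ρ²): 88 per arm at ρ = 0.3, then 107, 125 and 157 at ρ = 0.5, 0.6 and 0.7. That comparator is too weak, because section 5.d already collects PROMIS Pain Interference before treatment. The fair comparison is 80(1 − r²)/(1 − ρ²):

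- r = 0.5, ρ = 0.5: 80 × 0.75/0.75 = 80 (no gain)
- r = 0.5, ρ = 0.6: 80 × 0.75/0.64 = 94
- r = 0.3, ρ = 0.5: 80 × 0.91/0.75 = 97
- r = 0.3, ρ = 0.7: 80 × 0.91/0.51 = 143

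The last line pairs the weakest assumed substitute with the strongest assumed baseline. If correlation fades over the six weeks between baseline and last call, the relevant ρ lies towards the lower end.

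**Is validity at risk?** No. Randomisation makes a between-arm comparison of the call scores unbiased without a baseline. Only precision is affected.

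**The case for a change.** The strongest case for a change is that it is cheap and time-critical. One question at enrolment and a few sentences would fix the scale, the call days and one contrast, whereas a missed baseline is lost for good. The pilot is meant to support a funding application, so an undefined pain score invites selective reporting. The protocol also never says that the calls are only for monitoring.

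Part of this stands. The scale, recall period and call days are missing, *biweekly* is ambiguous, and the purpose of the score is unstated. Staff need one consistent question and a call schedule, which a call script and the REDCap form would ordinarily settle.

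The rest depends on treating the score as an outcome, which the documents never do. It shares a sentence and a telephone call with compliance and side effects. Promoting it would add an outcome to a plan that does not rank the ones it has. Its last call would fall close to the day-of-surgery PROMIS assessment, so it would add little on end-of-treatment pain. The risk of selective reporting is real only if the score is later presented as evidence of efficacy. Because neither 5.f nor 5.i lists it, a reader could see that such a result was not pre-specified.

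**Conclusion.** The observation is accurate, but no change to the plan is needed. Following the plan as written leads to no wrong or weaker conclusion on pain. The PROMIS Pain Interference comparison has its own baseline and between-arm contrast, and the calls do not enter it. What remains is operational detail that study staff can settle sensibly, plus the option of an extra outcome that the sponsor did not choose.

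The possible gain in precision concerns that extra outcome alone. Measured against the covariate already collected, it runs from zero to the equivalent of 63 more participants per arm (143 − 80) across the pairings shown. This rests on assumed correlations of 0.3 to 0.5 for PROMIS and 0.5 to 0.7 for the same score, none of which the documents give. None of it improves the planned PROMIS or synovial analyses.

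### Planned side-effect recording stops with the pre-operative phone calls: the last call has no fixed date, and no harms are systematically collected by arm from the day of surgery onward

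*Combined protocol and SAP*

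**What the plan says.** Section 5.g sets the exposure: "12mg Astaxanthin or placebo once daily for 6 weeks prior to surgery". Section 5.i places the second PROMIS assessment just ahead of the operation, as treatment finishes.

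Section 5.d contains the only planned side-effect recording: "Research staff will call participants biweekly over the 6-week period to assess pain score, supplement compliance and record any side effects". It does not say whether biweekly means every two weeks or twice a week, or when the last call falls.

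For the day of surgery, section 5.d lists two steps. The first is the questionnaire: "On the day of surgery, participants will again complete the PROMIS Physical Function and Pain Interference assessment when they arrive at the hospital". The second is the sample: "an aliquot of synovial fluid will be collected from the affected knee by the orthopedic surgeon performing the surgery". No side-effect question is listed and no later contact is described.

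Section 4 counts among the study documentation "operative reports, anesthesia reports, and post-operative progress notes available on the EPIC EMR". Section 6 lists known effects ("Possible side effects associated with Astaxanthin supplementation are increased bowel movements, red stool color, and stomach pain"), describes a possible hormone-related effect, and adds: "Astaxanthin has the potential to increase the function of your immune system".

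Section 5.f has no safety endpoint and section 5.i no analysis of harms. Section 5.l, whose title concerns subject safety, deals with data security, for example: "Data will be maintained on a secure server with password protection".

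**The concern.** Every participant is scheduled for a knee replacement directly after the treatment period. A collection window that closes with the pre-operative calls leaves out whatever begins between the last call and surgery, and whatever appears during or soon after the operation. Section 6 raises possible immune and hormone-related effects and does not say how long either would last after the last dose.

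At stake is the safety information that the pilot passes on. Section 1 presents the study as support for adding astaxanthin to symptom management in advanced osteoarthritis, and as groundwork for a large trial. If the plan is followed as written, the investigators could not describe peri-operative harms by arm, and silence on the subject could be taken as reassurance. Routine care will generate the relevant notes anyway, so the loss is avoidable.

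The point concerns only the length and definition of the collection window. The PROMIS and synovial comparisons do not depend on it.

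**Working it through.** The plan states no figure for harms, so there is none to reproduce. Three checks apply.

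**1. Doses after the last call.** Inputs: once-daily dosing for 6 weeks (5.g), so 6 × 7 = 42 doses on days 1 to 42; calls biweekly over that period (5.d). A call on a given day is taken to cover that day's dose. Doses after the last call = 42 − day of last call.

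| Reading of the schedule | Last call | Doses after it | Share of 42 |
|---|---|---|---|
| Every two weeks, end of each interval (days 14, 28, 42) | day 42 | 0 | 0% |
| Every two weeks, start of each interval (days 1, 15, 29) | day 29 | 13 | 31% |
| Every two weeks, no week-6 call (days 14, 28) | day 28 | 14 | 33% |
| Twice a week, second call at the end of each week | day 42 | 0 | 0% |
| Twice a week, calls early in each week | day 39 | 3 | 7% |

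The text allows all of these, so the range is 0% to 33%.

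**2. From the day of surgery onward.** Going through the sections in turn:

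- 5.d: questionnaire and synovial sample only; nothing afterwards.
- 5.f: PROMIS and synovial profiles only.
- 5.h: storage is described for PROMIS data, phone-survey data and synovial samples, with no chart-derived harms.
- 5.i: PROMIS and synovial analyses only.
- 5.l: data security and confidentiality only.
- 4: the peri-operative notes are named, but without who extracts from them, what is extracted, or until when.

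This gap does not depend on the meaning of biweekly.

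**3. What collection would yield.** Input: 80 per arm, 160 in total (5.c).

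- With zero events among n participants, the one-sided 95% upper limit is 1 − 0.05^(1/n). For n = 80 it is 3.7%; for n = 160 it is 1.9%.
- The chance of at least one event in an arm is 1 − (1 − p)^80. For p = 1%, 2%, 3% and 5% it is 55%, 80%, 91% and 98%.
- Power to separate 5% from 10% at two-sided 0.05 with 80 per arm is about 22%.

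The event rates are assumptions for illustration; the documents give none. The results show that the data would be descriptively useful but would not support a test between arms.

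**The case against.** The strongest reply is that the plan may lose little. Calls at weeks 2, 4 and 6 are a natural reading of section 5.d and leave no dose uncovered. Section 4 already counts the peri-operative notes as study documentation, so events would be on file. Neither the aims nor the endpoints concern peri-operative safety; the plan uses surgery as the time to repeat PROMIS and sample fluid. Section 6 calls the hormone-related effect unclear and names no peri-operative harm, and surgical notes are an unlikely place to find such symptoms.

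Much of this stands, and it rules out two stronger conclusions that a reader might draw. One is that harms from the final doses are bound to be missed: that does not follow, because a call at or near week 6 fits the text. The other is that peri-operative harms leave no trace in the study: that goes too far, because the notes are listed.

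The reply does not close the gap. A list of available records is not a collection procedure. Without an extraction step, a form and a cut-off, nothing ensures that both arms are examined in the same way. Even a call on the last dosing day cannot record an effect that starts later. For hormone-related symptoms, the day-of-surgery question is the useful part of the remedy, and it reaches only to that day.

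**Conclusion.** The concern holds in a limited form. Side effects are planned to be recorded only through the pre-operative calls, and the undefined schedule leaves 0 to 14 of 42 doses after the last one. The upper end is one permitted reading and should not be taken as the expected loss. From the day of surgery onward, no systematic by-arm collection of harms is specified under any reading.

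This rests on the text of sections 4 and 5.c to 5.l and on a count of one dose per day for 42 days. It assumes nothing about whether astaxanthin causes peri-operative harm, and the documents offer no evidence on that. The efficacy analyses are not affected. It is an inexpensive improvement that should be made, and it does not undermine the design.

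**What to change.** In section 5.d:

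- Define biweekly, and state when the last call falls relative to the last dose and surgery.
- Add the phone-call side-effect questions to the day-of-surgery iPad/REDCap session, covering the time since the last call.
- Have existing staff who are blinded to allocation extract intra-operative and post-operative complications for every participant from the EPIC notes listed in section 4. Use one form for both arms and a fixed cut-off stated in the protocol.

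In section 5.f, state that side effects are collected from first dose to that cut-off. In section 5.i, add a descriptive table of harms by arm, without a significance test.

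The cost is a few questions on an existing form, modest staff time for 160 chart extractions, and an amendment. The amendment should confirm that consent covers the post-operative extraction, since the consent form's wording was not available for this review. No extra visit, procedure or change to treatment is needed.
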